7.3 Mortality

Data collected for patient deaths will include whether the death occurred after withdrawal of care and, if so, the reason for withdrawal of care.

7.4 New Infections

Any new infections, regardless of the organism (e.g., viral or nonviral), should be captured on the eCRF. The site of infection and source of culture (e.g., sputum, blood, urine) should also be recorded.

8 SAFETY ASSESSMENTS

8.1 Safety Endpoints

The safety endpoints include the following:

- All cause TEAEs and SAEs;
- Change from screening (baseline) in clinical symptoms and abnormal vital signs, abnormal laboratory tests (e.g., complete blood count [CBC], serum chemistry, routine urinalysis, and coagulation function), and 12-lead electrocardiograms (ECGs); and
- Relationship of any observed AEs with F-652 treatment based on the Investigator's judgement.

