8.7 Clinical Laboratory Evaluations

CBC with differential will be performed at screening, Days 1, 3, 5, 7, 8, 10, 12, and 14. If the patient remains hospitalized, will also be performed on Days 15 and 29. If the screening assessment was obtained within 24 hours of Day 1 dosing, it is not necessary to repeat the CBC prior to Day 1 dosing.

Metabolic panel/chemistry assessments will be performed at screening, Days 1 and 8 (within 24 hours prior to dosing) and as clinically indicated. If the patient remains hospitalized, will also be performed on Days 15 and 29. If the screening assessment was obtained within 24 hours of Day 1 dosing, it is not necessary to repeat the chemistries prior to Day 1 dosing. Lactate dehydrogenase test should be repeated daily if elevated above the upper limit of normal.

Hemoglobin A1c will only be obtained at screening if the patient does not have a value within 90 days prior to screening.

Urine dipstick is acceptable and microscopic analyses can be performed if clinically indicated. If $\geq 2+$ protein on urine dipstick, then a spot urine sample should be collected in order to calculate the urine protein to creatinine ratio or a 24-hour urine should be collected.

Clinical laboratory analytes are listed in [Appendix B](#).

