8.9 Vital Signs

Vital signs will include systolic and diastolic blood pressure, respiration, pulse, and oral temperature, and should be taken prior to study drug infusion, every 15 minutes during the infusion, at the end of the infusion, and hourly post-infusion, for a minimum of 4 hours after each infusion within a window of ± 5 minutes. Vital signs should be collected on a daily basis and may be collected more frequently if clinically indicated. Patients should be in a sitting position for at least 5 minutes prior to collection.

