8.10 Electrocardiograms

Twelve-lead ECGs will be obtained at screening, Days 1 and 8 (pre-dose and 30 ± 10 minutes after the end of infusion) and as clinically indicated within a window of ± 10 minutes. If the patient remains hospitalized, will also be performed on Days 15 and 29. Whenever ECG and blood samples are specified to be collected at the same time, ECG will be obtained before the blood samples. ECGs should be obtained in digital format when possible and archived.

Patients should be in a supine position for at least 10 minutes prior to the ECG measurement. The ECG measurements will include heart rate, RR-interval, PR-interval, QT-interval, QRS-complex, and QTcF.

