9.2.3 Analysis of Safety

All safety analyses will be performed on the Safety Population.

AEs will be coded using the Medical Dictionary for Regulatory Activities (MedDRA) and summarized by system organ class, preferred term, and treatment arm as the number and percentage of patients with an event. The following subsets will also be summarized by treatment arm: TEAEs, treatment-related AEs, treatment-related SAEs, and AEs leading to drug discontinuation.

Changes from baseline in clinical laboratory data, ECGs, vital signs, and physical examination findings will be summarized with descriptive statistics by treatment arm.

All demographic data will be summarized using descriptive statistics (number of patients, mean, median, standard deviation, minimum, and maximum) for continuous variables and using frequencies and percentages for discrete variables.

A formal statistical analysis plan providing full technical details of the planned analyses will be finalized prior to database lock.

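### Safety change is defined from screening although later pre-dose Day 1 values are planned for ECGs, vital signs and most blood tests, so pre-treatment change enters the within-arm summaries

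*Combined protocol and SAP*

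**What the plan says.** The synopsis (Safety Endpoints) and Section 8.1 carry the same definition: "Change from screening (baseline) in clinical symptoms and abnormal vital signs, abnormal laboratory tests", followed by 12-lead ECGs. Section 9.2.3 gives the analysis: "Changes from baseline in clinical laboratory data, ECGs, vital signs, and physical examination findings will be summarized with descriptive statistics by treatment arm". It does not say what baseline means, and no other definition of the safety baseline is readable.

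The assessment sections plan values nearer to the first infusion:

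- ECGs (Section 8.10): "Twelve-lead ECGs will be obtained at screening, Days 1 and 8 (pre-dose and 30" minutes or so after the end of infusion. The Day 1 pre-dose tracing is unconditional.
- Vital signs (Section 8.9): these "should be taken prior to study drug infusion, every 15 minutes during the infusion", and again afterwards. The pre-infusion reading is also unconditional.
- Chemistry (Section 8.7): "Metabolic panel/chemistry assessments will be performed at screening, Days 1 and 8 (within 24 hours prior to dosing").
- CBC (Section 8.7): "CBC with differential will be performed at screening, Days 1, 3, 5, 7, 8, 10, 12, and 14".
- Waiver (Section 8.7): "If the screening assessment was obtained within 24 hours of Day 1 dosing, it is not necessary to repeat the CBC prior to Day 1", that is, before the first infusion. The same waiver is given for chemistry.

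Section 3.1 starts treatment on Day 1 after randomization. Section 9.1 counts analysis timepoints from the day of randomization.

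**The concern.** A change score meant to describe what happens on treatment should start from the patient's state just before treatment. Here the written rule starts it at screening, even where a later pre-dose value exists. The Section 8.7 waiver shows that the protocol allows screening to fall more than 24 hours before dosing. In that case it asks for a fresh blood sample, which Section 8.1 then does not use as the reference.

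The patients are hospitalized with moderate to severe COVID-19, so some movement before dosing is plausible, though the documents give no figure for it. Safety is part of the primary objective (Section 2.1), and the safety changes are reported descriptively by arm. A value that is normal at screening and already abnormal before the first infusion would read as a change on study. Each sentinel cohort has only 2 patients per arm, so chance differences in pre-treatment movement have little room to average out.

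**Working it through.** The plan gives no figure to reproduce. Two checks apply.

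**1. What the definition measures.** For any patient with both values:

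(post-dose − screening) = (Day 1 pre-dose − screening) + (post-dose − Day 1 pre-dose)

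The first term on the right occurred before any study drug. It enters the reported change with weight 1. Taking a true on-treatment change of 0 and assumed mean drifts between screening and Day 1:

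| Assumed drift (SD) | Within-arm change from screening (SD) | Within-arm change from Day 1 pre-dose (SD) | Expected difference between arms (SD) |
|---|---|---|---|
| 0 | 0 | 0 | 0 |
| 0.25 | 0.25 | 0 | 0 |
| 0.5 | 0.5 | 0 | 0 |

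The last column is 0 because drift before dosing has the same expectation in both arms under 1:1 randomization.

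**2. What it may do to precision.** The inputs are:

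- Patients per arm, pooled over the four cohorts (Section 3.1): 2 + 7 + 2 + 8 = 19, total 38.
- Correlation with the post-dose value: assumed 0.7 or 0.8 for Day 1 pre-dose and 0.4 to 0.7 for screening. None comes from the documents.
- Equal variance at each time, with SD set to 1 (assumed).

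The formulas are:

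- SD of change = √(2(1 − ρ))
- SE of the between-arm difference in mean change = SD of change × √(2/19)

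| ρ, Day 1 | ρ, screening | SE, Day 1 baseline | SE, screening baseline | Ratio |
|---|---|---|---|---|
| 0.7 | 0.4 | 0.251 | 0.355 | 1.41 |
| 0.7 | 0.5 | 0.251 | 0.324 | 1.29 |
| 0.7 | 0.6 | 0.251 | 0.290 | 1.15 |
| 0.7 | 0.7 | 0.251 | 0.251 | 1.00 |
| 0.8 | 0.4 | 0.205 | 0.355 | 1.73 |
| 0.8 | 0.5 | 0.205 | 0.324 | 1.58 |
| 0.8 | 0.6 | 0.205 | 0.290 | 1.41 |
| 0.8 | 0.7 | 0.205 | 0.251 | 1.22 |

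For example, with 0.8 and 0.4 the ratio is √(1.2)/√(0.4) = 1.095/0.632 = 1.73. The ratio depends only on the two correlations, not on the sample size.

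**The case against.** The best defence has four parts.

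- **The comparison is protected.** The study is randomized 1:1, double-blind and placebo-controlled, and safety changes are shown by arm. A reader might infer that a screening baseline biases F-652 against placebo. The documents do not support that, because drift before dosing is equal in expectation across arms. The summaries are descriptive, so no error rate is affected, and none of the stopping criteria in Section 4.3 is written as a change from baseline. All of this stands.
- **The gap may be short.** The eligibility criteria and the content of the Schedule of Procedures (Appendix A) are not readable, so the screening window is unknown. Where the laboratory screening sample fell within 24 hours of dosing and was not repeated, screening is itself the last pre-dose value and nothing is lost. This stands, and it is why the size cannot be fixed.
- **The derivation is left to a later SAP.** Section 9.2.3 leaves baseline undefined and promises full technical details before database lock. This stands only in part. An undefined term does not override an explicit definition given twice, and a SAP author following the protocol would use screening.
- **The reach is limited.** A reader might infer that a Day 1 pre-dose value exists for every safety measure. The readable text shows none for urinalysis, coagulation or clinical symptoms, and Section 8.11 does not say whether the Day 1 physical examination precedes dosing. With Appendix A not shown, this cannot be called a gap either. A reader might also extend the point to the NIAID scale, but Sections 7.1.1 and 9.2.1.1 say only that change is from baseline. Nothing ties that baseline to screening.

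**Conclusion.** The point holds for ECGs and vital signs in all patients, and for CBC and chemistry when screening was more than 24 hours before dosing. For these, the stated baseline is older than a value the protocol already collects. Pre-treatment change therefore passes in full into the within-arm summaries. It is a written rule that can be improved, not missing detail.

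The amount of drift cannot be computed from the documents. The precision effect is conditional: an SE ratio of 1.00 to 1.73 under the assumed correlations and equal variances. It applies to continuous measurements, and there is no gain if both pre-dose values predict the post-dose value equally well. It would be wrong to quote any single percentage as the expected gain. The consequence is confined to descriptive within-arm summaries and possibly precision, so this is a minor point and a free improvement.

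**What to change.** In the synopsis, Sections 8.1 and 9.2.3, and the SAP, define the safety baseline as the last non-missing value before the start of the first infusion. Screening is used only where no later pre-dose value exists. Changing Section 8.1 alone would leave the identical synopsis text in conflict with it.

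The rule needs no special case for the laboratory waiver: when the Day 1 sample is not repeated, screening is selected automatically. It also deals with measures whose Day 1 timing is unclear, provided assessment times are available to compare with the infusion time recorded under Section 5.5.4.

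The cost is a few lines of text, agreed before unblinding. It needs no additional patients, visits or samples.

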8.2 Adverse Events

An AE is defined as any untoward medical occurrence in a clinical investigation patient administered a pharmaceutical product, which does not necessarily have a causal relationship with this treatment. An AE can therefore be any unfavorable and/or unintended sign (including an abnormal laboratory finding), symptom, or disease temporally associated with the use of an investigational therapeutic product, whether or not related to the investigational therapeutic product. All AEs, including observed or volunteered problems, complaints, or symptoms, are to be recorded on the appropriate eCRF.

AEs, which include clinical laboratory test variables, will be monitored and documented from the time of informed consent to Day 60 or until all drug-related toxicities have resolved, whichever is later. Patients should be instructed to report any AE that they experience to the Investigator, whether or not they think the event is due to study treatment. Beginning at screening, Investigators should make an assessment for AEs at each visit and record the event on the appropriate AE eCRF.

Wherever possible, a specific disease or syndrome rather than the individual associated signs and symptoms should be identified by the Investigator and recorded on the eCRF. However, if an observed or reported sign or symptom is not considered a component of a specific disease or syndrome by the Investigator, it should be recorded as a separate AE on the eCRF. Additionally, the condition that led to a medical or surgical procedure (e.g., surgery, endoscopy, tooth extraction, or transfusion) should be recorded as an AE, not the procedure itself.

Any medical condition already present at screening should be recorded as medical history and not be reported as an AE unless the medical condition or signs or symptoms present at baseline changes in severity, frequency, or seriousness at any time during the study. In this case, it should be reported as an AE.

Clinically significant abnormal laboratory or other examination (e.g., ECG) findings that are detected during the study or are present at screening and significantly worsen during the study should be reported as AEs, as described below. The Investigator will exercise his or her medical and scientific judgement in deciding whether an abnormal laboratory finding or other abnormal assessment is clinically significant. Clinically significant abnormal laboratory values occurring during the clinical study will be followed until repeat tests return to normal, stabilize, or are no longer clinically significant. Abnormal test results that are determined to be an error should not be

reported as an AE. Laboratory abnormalities or other abnormal clinical findings (e.g., ECG abnormalities) should be reported as an AE if any of the following are applicable:

- If an intervention is required as a result of the abnormality;
- If action taken with the study drug is required as a result of the abnormality; or
- Based on the clinical judgement of the Investigator.

8.2.1 Adverse (Drug) Reaction

All noxious and unintended responses to a medicinal product related to any dose should be considered an adverse drug reaction. “Responses” to a medicinal product means that a causal relationship between a medicinal product and an AE is at least a reasonable possibility, i.e., the relationship cannot be ruled out.

8.2.2 Unexpected Adverse Drug Reaction

An Unexpected Adverse Drug Reaction is defined as an adverse reaction, the nature or severity of which is not consistent with the applicable product information.

8.2.3 Assessment of Adverse Events by the Investigator

The Investigator will assess the severity (intensity) of each AE according to the CTCAE grading system. The Investigator will also categorize each AE as to its potential relationship to study drug using the categories of yes or no.

The severity of all AEs should be graded according to the CTCAE v5.0. For those AE terms not listed in the CTCAE, the following grading system should be used:

- CTCAE Grade 1: Mild; asymptomatic or mild symptoms; clinical or diagnostic observations only; intervention not indicated;
- CTCAE Grade 2: Moderate; minimal local or noninvasive intervention indicated; limiting age-appropriate instrumental activities of daily living;
- CTCAE Grade 3: Severe or medically significant but not immediately life-threatening; hospitalization or prolongation of hospitalization indicated; disabling; limiting self-care activities of daily living;
- CTCAE Grade 4: Life-threatening consequences; urgent intervention indicated; or
- CTCAE Grade 5: Death related to the AE.

Causality assessment

The relationship of an AE to the administration of the study drug is to be assessed according to the following definitions:

No (unrelated, not related, unlikely to be related) – The time course between the administration of study drug and the occurrence or worsening of the AE rules out a causal relationship and another cause (concomitant drugs, therapies, complications, etc.) is suspected.

Yes (possibly, probably, or definitely related) – The time course between the administration of study drug and the occurrence or worsening of the AE is consistent with a causal relationship and no other cause (concomitant drugs, therapies, complications, etc.) can be identified.

The definition implies a reasonable possibility of a causal relationship between the event and the study drug. This means that there are facts (evidence) or arguments to suggest a causal relationship.

The following factors should also be considered:

- The temporal sequence from study drug administration-

The event should occur after the study drug is given. The length of time from study drug exposure to event should be evaluated in the clinical context of the event.

- Underlying, concomitant, intercurrent diseases-

Each report should be evaluated in the context of the natural history and course of the disease being treated and any other disease the patient may have.

- Concomitant drug-

The other drugs the patient is taking or the treatment the patient receives should be examined to determine whether any of them might be recognized to cause the event in question.

- Known response pattern for this class of study drug-

Clinical and/or preclinical data may indicate whether a particular response is likely to be a class effect.

- Exposure to physical and/or mental stresses-

The exposure to stress might induce adverse changes in the recipient and provide a logical and better explanation for the event.

- The pharmacology and PK of the study drug-

The known pharmacologic properties (absorption, distribution, metabolism, and excretion) of the study drug should be considered.

8.3 Serious Adverse Events

An AE or adverse reaction is considered serious if, in the view of either the Investigator or Sponsor, it results in any of the following outcomes:

- Death;
- A life-threatening AE;

Note: An AE or adverse reaction is considered “life-threatening” if, in view of either the Investigator or Sponsor, its occurrence places the patient at immediate risk of death. It does not include an event that, had it occurred in a more severe form, might have caused death.

- Requires hospitalization or prolongation of existing hospitalizations;

Note: Any hospital admission with at least 1 overnight stay will be considered an inpatient hospitalization. An emergency room or urgent care visit without hospital admission will not be recorded as an SAE under this criterion, nor will hospitalization for a procedure scheduled

or planned before signing of informed consent, or elective treatment of a pre-existing condition that did not worsen from baseline. However, unexpected complications and/or prolongation of hospitalization that occur during elective surgery should be recorded as AEs and assessed for seriousness. Admission to the hospital for social or situational reasons (i.e., no place to stay, live too far away to come for hospital visits, respite care) will not be considered inpatient hospitalizations.

- A persistent or significant disability/incapacity or substantial disruption of the ability to conduct normal life functions;
- A congenital anomaly/birth defect; or
- An important medical event.

Note: Important medical events that do not meet any of the above criteria may be considered an SAE when, based upon appropriate medical judgement, they may jeopardize the patient and may require medical or surgical intervention to prevent 1 of the outcomes listed above. Examples of such medical events include allergic bronchospasm requiring intensive treatment in an emergency room or at home, blood dyscrasias or convulsions that do not result in inpatient hospitalizations, or the development of drug dependency.

Events of progression of the patient's underlying COVID-19 diagnosis will be captured as efficacy endpoints; therefore, events clearly related to progression of the patient's underlying COVID-19 (signs/symptoms of progression) should not be reported as an SAE unless considered related to the study drug or the outcome is fatal during the study or within the safety reporting period. If the event has a fatal outcome during that timeframe, the event of "Progression of COVID-19" must be recorded as an SAE with a fatal outcome.

8.4 Serious Adverse Event Reporting – Procedures for Investigators

Initial reports

All SAEs occurring from the time of informed consent must be reported to Medpace Clinical Safety within 24 hours of the knowledge of the occurrence. After Day 60, any SAE that the Investigator considers related to study drug must be reported to Medpace Clinical Safety or the Sponsor/designee.

To report the SAE, complete the SAE form electronically in the electronic data capture (EDC) system for the study. When the form is completed, Medpace Safety personnel will be notified electronically by the EDC system and will retrieve the form. If the event meets serious criteria and it is not possible to access the EDC system, send an email to Medpace Safety at [contact] or call the Medpace SAE reporting line (phone number listed below), and fax/email the completed paper SAE form to Medpace within 24 hours of awareness. When the EDC system becomes available, the SAE information must be entered within 24 hours of the system becoming available.

Follow-up reports

The Investigator must continue to follow the patient until the SAE has subsided or until the condition becomes chronic in nature, stabilizes (in the case of persistent impairment), or the patient dies.

Within 24 hours of receipt of follow-up information, the Investigator must update the SAE form electronically in the EDC system for the study and submit any supporting documentation (e.g., patient discharge summary or autopsy reports) to Medpace Clinical Safety via fax or email. If it is not possible to access the EDC system, refer to the procedures outlined above for initial reporting of SAEs.

8.5 Pregnancy Reporting

If a patient becomes pregnant during the study, the Investigator is to stop dosing with study drug(s) immediately and the patient should be withdrawn from the study. Early termination procedures should be implemented at that time.

A pregnancy is not considered to be an AE or SAE; however, it must be reported to Medpace Clinical Safety within 24 hours of knowledge of the event. Medpace Clinical Safety will then provide the Investigator/site the Exposure In Utero (EIU) form for completion. The Investigator/site must complete the EIU form and fax/email it back to Medpace Clinical Safety.

If the female partner of a male patient becomes pregnant while the patient is receiving study drug, the Investigator should notify Medpace Clinical Safety as described above.

The pregnancy should be followed until the outcome of the pregnancy, whenever possible. Once the outcome of the pregnancy is known, the EIU form should be completed and faxed/mailed to Medpace Clinical Safety. If the outcome of the pregnancy meets the criteria for immediate classification as an SAE (i.e., postpartum complication, spontaneous abortion, stillbirth, neonatal death, or congenital anomaly), the Investigator should follow the procedures for reporting an SAE.

